7.8.2 Laboratory data

The analyses of laboratory data will be descriptive in nature and will be based on BI standards (9). It will include a graphical summary highlighting potential cases of Hy's Law.

The analysis of laboratory data will use the same 'analysing treatments' as described for the AEs, except for that the baseline laboratory value will be included in the 'on-treatment period'. Subjects having at least one post-baseline laboratory value will be displayed in the descriptive analyses. The following parameters are of particular interest:

- haematology: haemoglobin, white blood cell count, Absolute Neutrophil Counts, platelets
- Biochemistry: aspartate transferase, alanine transferase, bilirubin, serum creatinine, urea, sodium, potassium, magnesium
- Coagulation: international normalised ratio, partial thromboplastin time

Laboratory values: Baseline is defined as the latest time-point before the very first administration of study medication. A laboratory value on the same date as the first study drug administration is considered as according to protocol, i.e. as prior to first study drug administration and will therefore be used as baseline value.

The following outputs will be presented:

- Worst CTCAE grade experienced during the on-treatment phase.
- Transitions of CTCAE grade from baseline to worst laboratory value, from worst to last laboratory value on treatment and from baseline to last laboratory value during the on-treatment phase.

Worst laboratory value and its CTCAE grade (highest CTCAE grade) over all courses will be calculated for each laboratory parameter specified above.

The last laboratory value on treatment is the laboratory value of the last visit of the last course of each subject.

Furthermore, a summary table of possible clinically significant abnormalities will be given.

Possible clinically significant abnormal laboratory values are defined as those laboratory values that are of CTCAE grade ≥ 2 and show an increase from baseline value by at least one CTCAE grade. Frequency of subjects with possible clinically significant abnormal laboratory values will be provided whenever applicable. If no baseline value is available but the subject has a post-baseline laboratory value of CTCAE grade ≥ 2 an increase from baseline will be assumed, i.e. the laboratory value considered as possible clinically significant.

Hepatic injury:

As defined in the CTP a hepatic injury (DILI) is defined by the following alterations of hepatic laboratory parameters:

- an elevation of AST and/or ALT >3 fold ULN combined with an elevation of total bilirubin >2 fold ULN measured in the same blood draw sample, and/or
- marked peak aminotransferase (ALT, and/or AST) elevations ≥ 10 fold ULN

Potential Hepatic enzyme elevations (potential Hy's law cases): These are defined as those cases where a combination of all of the following events occurred: any on-treatment value of ALT and/or AST > 3 ULN with total bilirubin ≥ 2 ULN and ALKP < 2 ULN. The events can occur in any order, but must occur within 14 days of the previous event, i.e. the second event must occur within 14 days of the first event, and the third event must occur within 14 days of the second event, etc. Subjects with missing laboratory values for liver enzymes will be excluded from these analyses.

In addition, eDISH plot will be plotted to display the maximum on-treatment AST/ALT and maximum bilirubin in terms of ULN.

Neutrophil and platelet counts of each patients will be plotted in log scale graphs.

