3.3.3 Exclusion criteria

- 1) Acute promyelocytic leukemia (FAB subtype M3), according to WHO classification ([R09-2581](#)).
- 2) Patients who are candidates for allogeneic stem cell transplantation.
- 3) Active chronic graft versus host disease requiring immunosuppressive treatment.
- 4) Prior treatment with a hypomethylating agent (this also includes prior MDS treatment with decitabine or azazitidine).
- 5) Prior treatment with CD33 antibody.
- 6) Second malignancy currently requiring active therapy (except for hormonal/anti-hormonal treatment, e.g. in prostate or breast cancer).

Proprietary confidential information © 2019 Boehringer Ingelheim International GmbH or one or more of its affiliated companies

- 7) Current clinical central nervous system symptoms deemed by the Investigator to be related to leukemic CNS involvement (no lumbar puncture required, clinical assessment per Investigator's judgment is sufficient).
- 8) Aspartate amino transferase (AST) or alanine amino transferase (ALT) greater than $2.5 \times$ the upper limit of normal (ULN) or AST or ALT greater than 5 times the ULN for those with Gilbert syndrome.
- 9) Prothrombin time $> 1.5 \times$ ULN.
- 10) Total bilirubin $\geq 1.5 \text{ mg/dL} (> 26 \mu\text{mol/L})$ unless elevation is thought to be due to hepatic infiltration by AML, Gilbert syndrome, or hemolysis.
- 11) Serum creatinine $\geq 2.0 \text{ mg/dL}$.
- 12) Presence of concomitant intercurrent illness, or any condition which in the opinion of the Investigator, would compromise safe participation in the trial, e.g. active severe infection, unstable angina pectoris, new onset of exacerbation of a cardiac arrhythmia.
- 13) Psychiatric illness or social situation which in the opinion of the Investigator would limit compliance with trial requirements.
- 14) Known human immunodeficiency virus (HIV) infection or active hepatitis B virus or hepatitis C virus infection. Patients with any serological evidence of current or past hepatitis B exposure are to be excluded unless the serological findings are clearly due to vaccination.
- 15) Pregnant or breast feeding patients.

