Medical and scientific judgement should be exercised in deciding whether other situations should be considered serious reactions, such as important medical events that might not be immediately life threatening or result in death or hospitalisation but might jeopardise the patient or might require intervention to prevent one of the other outcomes listed above. Examples of such events are intensive treatment in an emergency room or at home for allergic bronchospasm, blood dyscrasias or convulsions that do not result in hospitalisation or development of dependency or abuse. Any suspected transmission via a medicinal product of an infectious agent is also considered a serious adverse reaction.

AEs considered “Always Serious”

In accordance with the European Medicines Agency initiative on Important Medical Events, Boehringer Ingelheim has set up a list of AEs, which by their nature, can always be considered to be “serious” even though they may not have met the criteria of an SAE as given above.

The latest list of “Always Serious AEs” can be found in the RDC portal. A copy of the latest list of “Always Serious AEs” will be provided to the Investigators/sites upon request. These events should always be reported as SAEs as described in [Section 5.3.9](#).

Adverse events of special interest (AESIs)

The term AESI relates to any specific AE that has been identified at the project level as being of particular concern for prospective safety monitoring and safety assessment within this trial, e.g. the potential for AEs based on knowledge from other compounds in the same class. AESI need to be reported to the Sponsor’s Pharmacovigilance Department within the same timeframe that applies to SAE, see [Section 5.3.9](#).

The following are considered as protocol-specified AESIs:

- Infusion-related reactions (CTCAE grade 3 or higher)
- Tumor Lysis Syndrome (any CTCAE grade)
- Any event that qualifies for DLT
- Drug Induced Liver Injury (DILI)

A hepatic injury (DILI) is defined by the following alterations of hepatic laboratory parameters:

- an elevation of AST and/or ALT \geq 3-fold ULN combined with an elevation of total bilirubin \geq 2-fold ULN measured in the same blood draw sample, and/or
- marked peak aminotransferase (ALT, and/or AST) elevations \geq 10-fold ULN

These laboratory findings constitute a hepatic injury alert and the patients showing these laboratory abnormalities need to be followed up according to the “DILI checklist” provided in the ISF.

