6. GENERAL ANALYSIS DEFINITIONS

6.1 TREATMENT(S)

Phase I

In the Phase I Part, treatments are not randomized (open-label, dose escalation). Different dose levels of the investigational medicinal product (BI 836858) can arise while combined with fixed dose of decitabine at 20 mg/m² per day. The data will be presented for all dose cohorts separately, in particular, subjects will be analysed by the dose cohort initially assigned in the first treatment course.

Table 6.1:1 Definition of analysing treatment periods

Analysing treatment period	Start date (including)	Stop date (excluding)
Screening	Date of informed consent	Date of first administration of trial medication
MTD evaluation period	Date of first administration of trial medication	First of start of the second treatment cycle or the end of the 30-day residual effect period
On-treatment	Date of first administration of trial medication	Start date of 'Follow-up'
Follow-up	Date of end of REP +1	Start date of 'Post-study'
Post-study	Last date subject status obtained / last date subject known to be alive + 1 (if subject is lost to follow-up) / date of refusal + 1 day / the date subject died + 1	During the trial: open / empty; after database lock (DBL): DBL + 1 day

Data recorded between the first administration of trial medication until up to 30 days (Residual effect period; REP) after the last administration of trial medication will be considered as on-treatment.

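### SAP 7.8.2 counts the pre-dose baseline laboratory value as on-treatment, so it can make or complete a potential Hy's law case or set an eDISH point

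*SAP*

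**What the plan says.** **Treatment period.** SAP 6.1 starts the on-treatment period at first dosing: "Data recorded between the first administration of trial medication until up to 30 days" after the last administration. SAP 7.8.2 departs from this for laboratory data. It uses the adverse-event periods "except for that the baseline laboratory value will be included in the" on-treatment period, and defines baseline as the last value before the very first study medication. The exception covers the laboratory analysis as a whole and is not confined to the transition tables.

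**Hepatic outputs.** SAP 7.8.2 defines a potential Hy's law case as "any on-treatment value of ALT and/or AST > 3 ULN with total bilirubin ≥ 2 ULN and ALKP < 2 ULN". The components may come in any order, each within 14 days of the one before. The eDISH plot shows each patient's maximum on-treatment AST/ALT and bilirubin in multiples of ULN. The laboratory definition of hepatic injury (DILI) names no period of its own.

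**Protocol alert.** Protocol 5.3.8.1 sets the alert at AST and/or ALT of at least "3-fold ULN combined with an elevation of total bilirubin" of at least 2-fold ULN in the same sample, or aminotransferases of at least 10-fold ULN.

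**Eligibility.** Exclusion 8 (Protocol 3.3.3) bars "Aspartate amino transferase (AST) or alanine amino transferase (ALT) greater than" 2.5 x ULN, or "AST or ALT greater than 5 times the ULN for those with Gilbert syndrome". Exclusion 10 bars total bilirubin of 1.5 mg/dL or more "unless elevation is thought to be due to hepatic infiltration by AML, Gilbert syndrome, or hemolysis", with no upper limit for those causes.

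**The concern.** Potential Hy's law cases and eDISH points are read one patient at a time as signs of drug-related liver injury. A value measured before any trial drug carries no such information. The eligibility criteria accept some patients with raised liver values, and the SAP then places their pre-dose sample inside the period from which cases are drawn.

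Other parts of the SAP do refer to baseline. Possible clinically significant abnormalities need a rise of at least one CTCAE grade (7.8.2), and the tumour lysis laboratory and creatinine criteria each use a relative baseline (7.8.1). The hepatic outputs have no such condition. The rule in 7.8.2 that a subject needs at least one post-baseline value to be displayed selects subjects; it does not remove their baseline value.

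**Working it through.** The plan gives no figure to reproduce, so the check sets eligibility against the case definitions.

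**1. Who can meet the limbs before dosing?** Inputs are the limits in exclusions 8 and 10, the protocol alert, and the Hy's law AST/ALT and bilirubin limbs. The documents give no bilirubin ULN; 0.7 to 1.3 mg/dL was assumed. The grid ran AST/ALT from 0 to 12 x ULN and bilirubin from 0 to 8 mg/dL, both in steps of 0.1. Counts below are grid cells at ULN 1.0 mg/dL, not patients.

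| Admitted as | Eligible cells | Bilirubin ≥ 2 x ULN | Protocol alert met | Hy's law AST/ALT and bilirubin limbs met |
|---|---|---|---|---|
| No exemption | 26 × 15 = 390 | 0 | 0 | 0 |
| Infiltration or hemolysis | 26 × 81 = 2106 | 26 × 61 = 1586 | 0 | 0 |
| Gilbert syndrome | 51 × 81 = 4131 | 51 × 61 = 3111 | 21 × 61 = 1281 | 20 × 61 = 1220 |

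At every assumed ULN, only patients with Gilbert syndrome can meet the alert or both Hy's law limbs at entry, with AST/ALT between 3 and 5 x ULN (above 3 for Hy's law). This reads the 5 x ULN limit as replacing 2.5 x ULN for them; otherwise that clause would have no effect. No exclusion concerns ALKP, so ALKP below 2 x ULN can also hold at baseline. Components from one sample are 0 days apart, inside the 14-day window.

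**2. Can baseline complete a case?** A patient exempt under exclusion 10 may enter with bilirubin of at least 2 x ULN. Protocol 5.3.6.1 schedules an additional safety laboratory on Day 10 of Cycle 1. If baseline was drawn on Day 1, that is 10 − 1 = 9 days later, so a Day 10 AST/ALT above 3 x ULN pairs with the baseline bilirubin even if bilirubin has since fallen below 2 x ULN. For eDISH no time window is stated, so the two maxima may be further apart. The laboratory DILI criterion needs one blood draw, so this route does not reach it.

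**3. When does counting baseline change the result?**

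| Pattern | Potential Hy's law case with baseline counted | With post-baseline values only |
|---|---|---|
| Gilbert, both limbs met at baseline and still met after dosing | Yes | Yes |
| Gilbert, both limbs met at baseline, one no longer met after dosing | Yes | No |
| Exempt, baseline bilirubin ≥ 2 x ULN and unchanged, AST/ALT rises above 3 x ULN | Yes | Yes |
| Exempt, baseline bilirubin ≥ 2 x ULN then below 2, AST/ALT above 3 x ULN within 14 days | Yes | No |

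ALKP below 2 x ULN is taken as met throughout. The count differs only in rows 2 and 4, where a limb met at baseline is not also met after dosing.

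**4. Size of one case.** The protocol synopsis gives 16 + 33 = 49 Phase I patients. One case is 1/49 = 2.0% overall, 1/16 = 6.3% of the escalation part or 1/33 = 3.0% of the extension.

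**The case against.** The strongest reply is that the effect is narrow and the outputs are only descriptive. The label is potential cases, no hypothesis is tested, and baseline has a natural place in the transition tables. Laboratory analyses also follow a sponsor standard (SAP reference 9) that is not available here and might restrict these outputs. The narrowness stands. However, 7.8.2 words the exception for laboratory analysis generally, and a reader of the SAP alone would programme it that way.

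Four stronger readings are tempting, and the documents do not support them.

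- *A patient whose raised values persist, or whose AST/ALT rises at unchanged raised bilirubin, is a case created by the baseline rule.* Such a patient qualifies on post-dose samples alone (rows 1 and 3).
- *Every patient exempt under exclusion 10 starts with the bilirubin limb met.* The exclusion begins at 1.5 mg/dL and the limb at 2 x ULN. For an assumed ULN of 1.0 to 1.2 mg/dL the limb is 2.0 to 2.4 mg/dL, so an exempt patient at 1.6 mg/dL does not meet it. All exempt patients would meet it only if ULN were at most 1.5/2 = 0.75 mg/dL.
- *Counts of DILI as an adverse event of special interest are inflated too.* Protocol 5.3.9 treats pre-existing abnormalities as baseline conditions, SAP 7.8.1 assigns events before first intake to screening, and the baseline exception is limited to laboratory data.
- *Exclusions 8 and 10 contradict the alert.* The alert triggers follow-up: "These laboratory findings constitute a hepatic injury alert and the patients showing these laboratory abnormalities need to be followed up". An entry limit that overlaps a follow-up alert is not a contradiction, and recruitment is closed, so changing the eligibility text would alter no result.

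**Conclusion.** The point holds in limited form. As written, SAP 7.8.2 lets a pre-dose value make a potential Hy's law case (Gilbert syndrome, AST/ALT above 3 and up to 5 x ULN, bilirubin at least 2 x ULN), complete one (exempt patient, raised baseline bilirubin that later falls, AST/ALT above 3 x ULN within 14 days), or set an eDISH point. The laboratory DILI output is exposed only through the Gilbert route.

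The number of patients who entered under the exemptions is not given, and the number whose classification would change is probably small and may be zero. One would be 2.0% of 49. It still merits correction because each potential Hy's law case is interpreted individually in the first clinical study of this combination. The conclusion rests on the literal text of 7.8.2 and on the sponsor's laboratory standard not overriding it. The Gilbert finding does not depend on the assumed bilirubin ULN within 0.7 to 1.3 mg/dL.

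**What to change.** In SAP 7.8.2:

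1. Derive potential Hy's law cases, the laboratory-based hepatic injury (DILI) output and the eDISH maxima only from values after the first administration of trial medication.
2. Keep the baseline value for the CTCAE transition tables, where it is the starting point.
3. Flag in these three outputs any patient whose baseline already meets the AST/ALT or the bilirubin limb. Step 1 alone leaves persistent pre-existing elevation among the cases; the flag lets a reader tell it from new onset without hiding any patient.
4. State one rule for samples taken on the first dosing day. SAP 6.7 decides by clock time where it is recorded, while 7.8.2 treats every same-day value as pre-dose, so post-baseline is not yet uniquely defined.

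The cost is a few lines of SAP text, one date-time filter and one flag. No new data are needed. The case count can only stay the same or fall.

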5.3.6 Safety laboratory parameters

5.3.6.1 General safety laboratory parameters

Blood samples and urine have to be collected at the time points specified in the [Flow Chart](#). All safety laboratory examinations will be performed at the Investigator's local laboratory and include hematology, biochemistry, coagulation and qualitative urine analysis:

Hematology	Hemoglobin, white blood cell count (WBC) with differential count, platelets
	Reticulocytes have to be measured only at Visit 1 of every second cycle, EOT and EoR visit
Biochemistry	Glucose, sodium, potassium, calcium, inorganic phosphate, creatinine, aspartate amino transferase (AST), alanine amino transferase (ALT), alkaline phosphatase (AP), lactate dehydrogenase, total bilirubin, urea (preferred) or BUN, total protein, albumin, uric acid, C-reactive protein (CRP). Serum immunoglobulin levels (IgG, IgM, IgA) and direct antiglobulin test have to be measured only every other cycle (starting on Day 1 of Cycle 1) and at the EOT visit.
Coagulation	Activated partial thromboplastin time, prothrombin time, international normalized ratio where indicated (e.g. treatment with vitamin K antagonists)
Urine	pH, glucose, erythrocytes, leukocytes, protein, nitrite will be analyzed by dipstick and reported as semiquantitative measurements at screening, completion of Cycle 4 and at EOT visit. In case of pathological findings, further evaluation should be performed and results documented.
Pregnancy test	A serum pregnancy test needs to be obtained at the time points indicated in the Flow Chart in patients of childbearing potential.

Monitoring for laboratory evidence of tumor lysis syndrome

Tumor lysis syndrome (TLS) is characterized by a group of metabolic derangements caused by the massive and abrupt release of cellular components into the blood after rapid lysis of malignant cells, potentially leading to hyperuricemia, hyperkalemia, hyperphosphatemia, hypocalcemia, and uremia ([R10-4517](#)). To allow for early treatment in case TLS develops, vigilant monitoring is mandatory.

Parameters for TLS screening are included in the routine safety labs. Additional blood samples for TLS monitoring have to be obtained at the time points in Cycle 1 indicated in [Table 1](#), further samples may be obtained as clinically indicated. Sampling for TLS in course

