2 and subsequent courses should be performed as clinically indicated. The actual date and time of the blood samples should be recorded in the electronic Case Report Form.

Blood sampling to screen for laboratory evidence of TLS should include:

Haematology: haemoglobin, white blood cell count (WBC) with differential and blast count, platelets (PLT)

Biochemistry: uric acid, potassium, calcium, inorganic phosphate, lactate dehydrogenase (LDH), creatinine, urea

An additional safety laboratory will be collected on Day 10 of Cycle 1 (i.e. approximately 24 h after start of the first administration of BI 836858). Other laboratory tests to be included: haptoglobin and direct antiglobulin test. Non pre-existing abnormal laboratory values (CTCAE grade 3 or higher) will be followed up every 48 h until these laboratory values are back to at least CTCAE grade 1.

In case an administration is delayed due to an AE, the patient should visit the site at least once a week for assessment of safety laboratory and AEs. More frequent visits may be appropriate as assessed by the Investigator.

[REDACTED]

5.3.7 **Electrocardiogram (ECG)**

A 12-lead resting ECG will be performed in all patients according to the schedule in the [Flow Chart](#). The ECG will be assessed for pathological results (to be recorded as either concomitant disease or AE) by the Investigator. Additional examinations should be done whenever the Investigator deems necessary.

5.3.8 **Assessment of adverse events**

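### The SAP's worst-grade laboratory list names magnesium, omits uric acid, phosphate, calcium and LDH, and no output counts patients who meet only the laboratory part of the tumour lysis rule

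*SAP*

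**What the plan says.** SAP 7.8.2 introduces its laboratory list with "The following parameters are of particular interest". The biochemistry line names the two transaminases and bilirubin, and then "serum creatinine, urea, sodium, potassium, magnesium". Further down, the worst value and its CTCAE grade over all courses "will be calculated for each laboratory parameter specified above". The same section plans CTCAE grade transitions between baseline, worst and last value. It then adds a table of clinically significant abnormalities, defined by a grade of 2 or more and a rise of at least one grade from baseline.

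Protocol 5.3.6.1 gives the routine panel as "Glucose, sodium, potassium, calcium, inorganic phosphate, creatinine, aspartate amino transferase (AST), alanine amino transferase (ALT), alkaline phosphatase (AP), lactate dehydrogenase, total bilirubin", followed by "urea (preferred) or BUN, total protein, albumin, uric acid, C-reactive protein (CRP" and some less frequent tests. Its TLS sampling is listed as "Biochemistry: uric acid, potassium, calcium, inorganic phosphate, lactate dehydrogenase (LDH), creatinine, urea". Protocol 4.2.1 makes TLS laboratory monitoring mandatory. The amendment description in Protocol section 11 gives a fatal TLS case as the reason for splitting the first BI 836858 dose, and calls the added TLS monitoring an urgent safety measure.

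SAP 7.8.1 has a separate rule for potential TLS with two criteria, both required:

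- Criterion (1): at least two of uric acid, potassium, inorganic phosphate and calcium meet the limits in Table 7.8.1:3, in the window from the infusion day to six days after, with two qualifying values in the same 24 hours.
- Criterion (2): an adverse event from the searches in Table 7.8.1:4, or a qualifying creatinine rise, at any time in the treatment or residual effect period.

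**The concern.** The list is more than emphasis, because one output is expressly built from it. If it does not match what is collected, the program plans a row for an analyte that the protocol does not schedule and has none for most of the TLS panel. The final SAP is dated 19 November 2019, after that monitoring was added.

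What is at stake is the description of a known and serious risk. A reader of the report will want to know how far uric acid, phosphate, calcium and LDH moved, and how many patients showed the laboratory pattern of tumour lysis without a recognised clinical picture. The second question is not answered by a rule that flags only patients who meet both criteria.

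**Working it through.** No sample size, rate or error probability is involved. The check sets the lists side by side and then asks which outputs depend on the SAP list.

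**Step 1: lists compared.** Inputs are the SAP 7.8.2 biochemistry line (8 parameters), the routine and TLS biochemistry panels in Protocol 5.3.6.1 (the latter with 7 parameters), and SAP Table 7.8.1:3 (4 parameters).

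| Analyte | SAP 7.8.2 list | Protocol routine panel | Protocol TLS panel | SAP TLS rule, criterion (1) |
|---|---|---|---|---|
| Magnesium | yes | no | no | no |
| Potassium | yes | yes | yes | yes |
| Creatinine | yes | yes | yes | no (used in criterion 2) |
| Urea | yes | yes (or BUN) | yes | no |
| Uric acid | no | yes | yes | yes |
| Inorganic phosphate | no | yes | yes | yes |
| Calcium | no | yes | yes | yes |
| LDH | no | yes | yes | no |

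- On the SAP list but in neither written panel: 1 of 8 (magnesium).
- In the TLS panel but not on the SAP list: 7 − 3 = 4 (uric acid, phosphate, calcium, LDH).
- In criterion (1) but not on the SAP list: 4 − 1 = 3 (uric acid, phosphate, calcium).
- Named in no visible SAP output: LDH.

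**Step 2: which outputs use the list.** The worst value and worst grade do so explicitly. The transition tables are not tied to it in words, but two of their three comparisons use the worst value, so on a natural reading they share the restriction. The table of clinically significant abnormalities carries no parameter list.

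**Step 3: can another output give the laboratory-only TLS count?** The abnormality table is the nearest candidate. It differs from criterion (1) in three ways:

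- Baseline: the last value before the very first study drug, against the last value before each BI 836858 infusion.
- Threshold: CTCAE grade 2 or more with a grade increase, against absolute limits, combined with a 25% change for three of the four analytes.
- Pairing: none, against two analytes within 24 hours.

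The missing pairing alone is decisive. If a of the 16 + 33 = 49 Phase I patients are abnormal for one analyte and b for another, the number abnormal for both can be anything from max(0, a + b − 49) to min(a, b), and the number abnormal for both within 24 hours can be lower still. Separate frequencies cannot fix it.

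**The case against.** The strongest reply is that little is lost. The list is headed as a matter of interest, not exclusion. The abnormality table is not limited to it, and Protocol 7.3.4 commits to reporting all abnormalities of potential clinical significance. Potassium, itself a TLS sign, is on the list. Laboratory changes that the investigator considers clinically relevant are recorded as adverse events (Protocol 5.3.9). TLS of any grade is an adverse event of special interest, and such events are tabulated. Uric acid, phosphate and calcium are used in Table 7.8.1:3, which is more specific to TLS than a worst grade over all courses. Section 7.8.2 also rests on an internal standard that is not available here.

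Most of that stands, and it rules out three stronger readings:

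- A reader might infer that isolated laboratory signs are summarised nowhere. The abnormality table and the adverse event tables contradict this, although the former gives frequencies only where applicable and its coverage is not spelled out.
- A reader might infer that the TLS rule always needs a clinical event. It does not: a qualifying creatinine rise satisfies criterion (2). That criterion also uses broad searches over a long window, so many patients with the laboratory pattern may meet it.
- A reader might infer that the magnesium row must be empty. That is not shown. Testing is local, unscheduled visits can record relevant results, and the protocol's Table 1 is not in the text available. Protocol 1.2.2 names low magnesium among common events with decitabine, so an interest in it is understandable.

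The reply does not supply the count of patients who meet criterion (1) alone. The adverse event route depends on the investigator's opinion, and the abnormality table does not pair analytes in time. No section promises this count, so it is a recommendation rather than a broken commitment.

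**Conclusion.** The mismatch is established from the written text: one of eight listed biochemistry parameters is not in the protocol panels, and four of seven TLS biochemistry parameters are missing from the list that drives the worst-value and worst-grade outputs. The consequence is limited. These analytes have other routes into the report, but no described output gives the number of patients with the laboratory pattern only, and LDH is named nowhere in the SAP's outputs. This is a minor point, worth correcting because the risk concerned is one for which the protocol was amended.

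The conclusion assumes that the written panels in Protocol 5.3.6.1 are complete for magnesium, that the transition tables follow the same list as the worst values, and that no blacked-out SAP section or internal standard adds the missing outputs. The number of patients with the laboratory pattern alone is unknown.

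**What to change.** In SAP 7.8.2:

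- Remove magnesium from the list, or state where it is collected.
- Add uric acid, inorganic phosphate, calcium and LDH to the worst-value outputs. Give CTCAE grade and transitions only where a grade exists. The documents do not show that LDH has one, so for LDH the worst value may be all that can be given.
- State whether the table of clinically significant abnormalities covers every collected parameter.

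In SAP 7.8.1, report by dose cohort the number of patients who meet TLS criterion (1) alone, next to the number who meet both criteria.

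The data are already collected and criterion (1) has to be programmed for the existing rule, so the cost is an edit to a parameter list and a few extra table rows.
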